### **13.5 Exploratory Analyses**

#### Assessment of Exploratory Variables:

Exploratory markers will be taken at baseline and every 3 months during the study.

The exploratory variables will be summarized using descriptive statistics. The descriptive statistics will include the actual values and the changes from baseline for the exploratory variables.

### **13.6 Safety Analysis**

Assessment of safety will be based on the incidence of AEs, AEs resulting in discontinuation, and serious adverse events (SAEs) in each dose level. AEs will be coded using the Medical Dictionary for Regulatory Activities (MedDRA). Summaries of AEs will be provided showing the number and percentage of subjects who experienced at least 1 AE. These summaries will be presented by dose level, system organ class, and the preferred term. The occurrence of AEs will also be tabulated by severity and relationship to study medication. SAEs and AEs resulting in discontinuation will be summarized separately. All vital sign measurements, clinical laboratory results, pain score, and ECG findings will be summarized by dose level and time point using descriptive statistics or frequency distributions.

All safety summaries will be performed by dose levels and by all subjects.

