## 1 SYNOPSIS (EXPANDED/PHASE II)

Name of Sponsor/Company: Suzhou Kintor Pharmaceutical, Inc.
Name of Investigational Product: Proxalutamide (GT0918)
Title of Study:  An Expanded/Phase II, Multi-Center, Randomized, Open-Label Study to Evaluate the Safety and Tolerability of Proxalutamide (GT0918) in Subjects with Metastatic Hormone Sensitive Prostate Cancer (mHSPC) or Metastatic Castrate Resistant Prostate Cancer (mCRPC) who Failed Either Abiraterone or Enzalutamide
Study period:  Date first subject enrolled: 2Q2019
Phase of development (2nd stage): Expanded/Phase II
Objectives (Expanded/Phase II):

Primary:
 
 
• Evaluate the safety and tolerability of GT0918 in subjects with mHSPC or mCRPC who failed either abiraterone or enzalutamide treatment and determine the Recommendation Phase II Dose (RP2D) for other Phase II or III studies.
 
 
Secondary:
 
 
• To evaluate radiographic progression-free survival (rPFS)
 
• To evaluate objective response rate
 
• To evaluate time to radiographic progression
 
• To evaluate Prostate Surface Antigen (PSA) 50% decline and maximum change at 12 weeks
 
• To evaluate PSA doubling time (PSA DT)
 
• To evaluate the time to PSA progression
 
• To identify exploratory biomarkers to characterize androgen receptor (AR) inhibition and/or down-regulation by GT0918
 

Study Design (Expanded/Phase II):  This study is an open-label, randomized, expanded/phase II study in subjects with mHSPC or mCRPC who progressed after either abiraterone or enzalutamide treatment. All subjects will be randomized to take 400 mg or 500 mg of GT0918 by oral administration once daily on an empty stomach (2-3 hours after a meal) for initial treatment of 6 months. Randomization of subjects will be stratified by prior therapy (abiraterone or enzalutamide).  Subjects will continue treatment with GT0918 for up to 24 additional cycles (total up to 30 cycles) at their assigned dose on an empty stomach until disease progression, intolerable toxicities/adverse events

Suzhou Kintor Pharmaceutical, Inc.  
Protocol#: GT0918-US-1002

Proxalutamide (GT0918)

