### 8.6.3 Dose modification and missing dose

Treatment modifications will be made based on specified safety criteria. Subjects may skip or discontinue treatment with GT0918 if they experience at least one adverse event, (noted below), following their dose of GT0918, and are considered by the Investigator to be **“possibly”**, **“probably”** or **“definitely”** related to study drug. Treatment modifications must be reported to the project team and discussed with the assigned medical monitor.

- 1) For any subjects experiencing grade 3 or 4 hematologic and/or biochemical toxicity, study drug will be temporarily interrupted until toxicity resolves to grade 1 or better
- 2) For any subjects experiencing grade 2 non-hematologic toxicity with significant impact on subject's daily active life, such as asthenic condition (including asthenia and fatigue), hepatotoxicity, mental impairment and anxiety, study drug will be temporarily interrupted until toxicity resolves to grade 1 or better
- 3) If the Investigator considers that continuing study drug is clinically beneficial for the subjects, the treatment and dose can be resumed. For some subjects if dose reduction is safe and clinically appropriate, a dose range of 25-50% dose reduction from original starting dose can be considered. The dose modification and schedule must be

Suzhou Kintor Pharmaceutical, Inc.  
Protocol#: GT0918-US-1002

Proxalutamide (GT0918)

discussed prior to implementation with the assigned medical monitor. Possible dose reductions are proposed as follow.

- i. For dose cohort of 400mg: starting dose can be 200mg or 300mg
- ii. For dose cohort of 500mg: starting dose can be 300mg or 400mg

**Dose restoration:** If any subjects on reduced dose for 2 cycles or more, the subject will have an option for the dose modification, for example, either to remain on the same dose or increase one dose level up or resume initial dose. The dose modification shall be considered based on investigator's clinical judgement for the best interest and care of subject and it must be discussed with medical monitor before implemented and document CRF timely and properly.

The subject may discontinue study drug for up to 5 consecutive days without being discontinued for noncompliance, which is at the investigator's discretion and is to be noted on the eCRF.

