## 13 STATISTICAL ANALYSIS

A Statistical Analysis Plan (SAP) will be prepared after the protocol is approved. This document will provide further details regarding the definition of analysis variables and analysis methodology to address all study objectives. The SAP will serve as a compliment to the protocol and supersedes it in case of differences.

The statistical evaluation will be performed using the Statistical Analysis Software (SAS®) Version 9.4 or higher (SAS Institute, Cary, NC). All data will be listed, and summary tables will be provided. Summary statistics will be presented by dose group. For continuous variables, data will be summarized with the number of subjects (N), mean, standard deviation, median, minimum, and maximum by treatment group. For categorical variables, data will be tabulated with the number and percentages of subjects for each category by treatment group. No interim analyses are planned for the Phase II dose expansion study.

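### AE tables use crude percentages over exposure of 1 dose to 30 cycles, by an undefined dose level, so any difference in time on drug can distort the 400 v 500 mg contrast in either direction

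*Combined protocol and SAP*

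**What the plan says.** Section 13.6 sets the basis of the safety assessment: "Assessment of safety will be based on the incidence of AEs, AEs resulting in discontinuation, and serious adverse events (SAEs) in each dose level". The AE measure is a crude subject count: "Summaries of AEs will be provided showing the number and percentage of subjects who experienced at least 1 AE". On grouping it says "These summaries will be presented by dose level, system organ class, and the preferred term" and, at the end, "All safety summaries will be performed by dose levels and by all subjects". AEs are also tabulated by severity and relationship, and SAEs and AEs leading to discontinuation are summarised separately. Vital signs, laboratory results, pain score and ECG are "summarized by dose level and time point using descriptive statistics or frequency distributions". The opening of Section 13 uses another term: "Summary statistics will be presented by dose group".

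The exposure behind these tables is set elsewhere:

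- Section 13.2 admits any subject with one dose to the safety set.
- The Synopsis (Study Design) allows "up to 24 additional cycles (total up to 30 cycles". Section 9.2.3 still speaks of 18 further cycles; the two must be reconciled.
- Section 12.5.1 collects AEs from first dose to last dose or the end-of-study visit, so observation time grows with treatment time. The 30-day window afterwards is for drug-related events.
- Section 8.6.3 permits dose reduction, "For dose cohort of 500mg: starting dose can be 300mg or 400mg", and later re-escalation.

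Section 5.1 selects the RP2D on safety, tolerability and dose exposure. Section 5.2 compares 400 mg with 500 mg over six months or more, with no upper limit. Section 13 contains no exposure-adjusted AE rate, time-to-first-AE analysis, common AE window, or summary of exposure or dose intensity.

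**The concern.** The percentage of subjects with an AE depends on how toxic the drug is and on how long each subject is watched. Here the second part follows time on drug, which ends at progression, toxicity or withdrawal and so may itself depend on dose. If the two arms differ in time on drug, the crude percentages mix toxicity with duration. An arm can look worse because its subjects stayed longer, or acceptable because they left sooner. The second error is arguably the more serious when choosing a dose.

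The grouping adds a separate ambiguity. If *dose level* means the randomised arm, the randomised comparison is kept. If it means the dose being taken, a subject reduced from 500 to 400 mg moves into the other arm's column, can be counted in both, and the comparison is no longer randomised.

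Safety and tolerability by dose is the primary objective, and no interim analysis or data monitoring committee is planned. The end-of-study tables therefore carry much of the prespecified evidence for the dose choice.

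**Working it through.** **The plan's own figure.** The only planning number in Section 13 is 60 subjects. It checks as 2 × 30, and as the Synopsis's 4 × 15. No AE rate, power or exposure assumption lies behind it, and it is not disputed. All hazards and times on drug below are therefore assumptions.

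**Inputs from the protocol.** Cap of 30 cycles × 28 days = 840 days = 27.6 months; first 6 cycles = 168 days = 5.5 months; 30 subjects per arm.

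**Formula.** With a constant AE hazard h, exponential time on drug with stopping rate s, and cap T:

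crude incidence = h/(h+s) × [1 − exp(−(h+s)T)]

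Here s = ln 2 / median, or 1 / mean (the mean before the cap is applied). The standard error (SE) of a difference at 30 per arm is √{[p₁(1−p₁) + p₂(1−p₂)]/30}. Gaps are taken before rounding.

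**1. Equal hazard in both arms, median time on drug 4 v 8 months.** The stopping rates are 0.1733 and 0.0866 per month.

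| Hazard | 4 months | 8 months | False gap | SE |
|---|---|---|---|---|
| 3%/month | 0.03/0.2033 × 0.996 = 14.7% | 0.03/0.1166 × 0.960 = 24.7% | 10.0 points | about 10 |
| 5%/month | 0.05/0.2233 × 0.998 = 22.3% | 0.05/0.1366 × 0.977 = 35.7% | 13.4 points | about 12 |

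**2. Range over other assumptions.** Equal hazard per cycle, mean time on drug in cycles, cap 30.

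| Hazard per cycle | 6 v 9 cycles | Gap (SE) | 6 v 12 cycles | Gap (SE) |
|---|---|---|---|---|
| 0.02 | 10.7% v 15.0% | 4.3 (8.6) | 10.7% v 18.5% | 7.8 (9.1) |
| 0.05 | 23.0% v 30.8% | 7.7 (11.4) | 23.0% v 36.8% | 13.8 (11.7) |
| 0.10 | 37.5% v 47.3% | 9.8 (12.7) | 37.5% v 54.3% | 16.8 (12.7) |

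The false gap runs from about 4 to 17 points. With equal exposure it is zero.

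**3. Masking.** Suppose the hazard is 0.075 per cycle at 500 mg and 0.05 at 400 mg (ratio 1.5), with mean time on drug 6 cycles at 500 mg and 9 at 400 mg.

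- 500 mg: 0.075/(0.075 + 0.1667) × 0.999 = 31.0%
- 400 mg: 0.05/(0.05 + 0.1111) × 0.992 = 30.8%

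The excess disappears from the crude table. Events per person-time at risk would recover 0.075/0.05 = 1.5.

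**4. Where the distortion is small.** For an AE confined to cycle 1 (hazard 0.3 in that cycle only), means of 6 v 12 cycles give 24.0% v 24.9%. Summaries by time point do not accumulate over treatment, so the argument hardly reaches them.

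**5. First 6 cycles only.** The 5%/month case falls from 22.3% v 35.7% to 15.9% v 19.4%. The 0.05 per cycle case with means 6 v 12 falls from 23.0% v 36.8% to 16.8% v 20.7%. The gap shrinks to between 3 and 4 points but stays, because subjects can stop before day 168.

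**6. Dose reduction under grouping by randomised arm.** If 20% or 40% of 500 mg person-time is at a reduced dose carrying the 400 mg hazard, a true rate ratio of 1.5 appears as (0.8 × 0.075 + 0.2 × 0.05)/0.05 = 1.4, or (0.6 × 0.075 + 0.4 × 0.05)/0.05 = 1.3. That is a fair contrast of the two starting doses as managed. It is also why AEs by dose at onset and dose intensity should be shown beside it.

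**The case against.** The strongest reply is that the distortion is conditional. A reader might infer that the longer-treated arm will look more toxic in this trial. The documents do not support that: both arms have the same cap and stopping rules, nothing predicts different time on drug for doses of 400 and 500 mg, and the bias can go the other way. This stands.

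A reader might also infer that the plan mixes the arms. It does not say so. Section 13 refers to dose group and treatment group, Sections 6.2 and 9.2.3 to the assigned dose level, and Section 8.6.3 still names the 500 mg cohort when describing its reductions. But Section 8.6.3 also uses dose level for the dose being taken when it describes re-escalation. The term is therefore undefined, with the weight of the wording towards the randomised arm.

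Third, Section 13.6 is not limited to at-least-one-AE percentages. It adds severity, relationship, SAE and discontinuation tables. This also stands, although those AE tables have no person-time denominator either.

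Fourth, the illustrated gap is about 1 SE, in descriptive tables with no planned between-arm test, and safety is also reviewed during the study. That limits the consequence. But a systematic error as large as the sampling error is still worth removing when the remedy is cheap.

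Last, Section 13 defers detail to a later SAP that supersedes the protocol. No separate SAP text is in the supplied document, so it may cover this; it is a suitable place for the fix.

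**Conclusion.** The point holds in conditional form and should be acted on. Section 13.6 gives crude AE incidence over very unequal exposure, with no person-time denominator, while the primary endpoint names dose exposure as a basis for the RP2D. If time on drug differs between arms, the AE contrast for events with continuing risk is distorted in either direction. The size is a false gap of 10 to 13 points for medians of 4 v 8 months and hazards of 3 to 5% per month, about 4 to 17 points over the wider range tried, or complete masking of a 1.5-fold hazard. These figures rest on assumed constant hazards and exponential time on drug; none comes from the protocol.

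Two limits belong with the conclusion. It concerns AEs with continuing risk, not early-onset AEs or the summaries by time point. And a reader might take the first 6 cycles as a period common to all subjects and hence a complete remedy. Section 7.3 lets subjects leave earlier, so that window reduces the distortion without removing it, and it leaves out later toxicity.

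The undefined *dose level* is a separate gap: only a received-dose reading would break the randomised comparison, but the text does not exclude that reading.

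**What to change.** In Section 13.6, or in the SAP:

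1. State that safety is summarised by randomised arm (starting dose), and use one term throughout Section 13. Show AEs by dose at onset as supportive only.
2. Keep the crude full-period AE tables. Beside them, add exposure-adjusted incidence (subjects with the event per 100 patient-months at risk, time at risk ending at the first event) and time to first grade 3 or higher AE. Read the crude and adjusted results together, since a single rate assumes a roughly constant hazard and suits early-onset AEs poorly.
3. Summarise exposure and dose intensity by arm, including reductions, interruptions and re-escalations. This also supplies the exposure evidence that Section 5.1 calls for.
4. Add a cycles 1-6 AE table as a supplement, with a note that it reduces but does not remove the distortion.
5. Reconcile the number of additional cycles between the Synopsis (24) and Section 9.2.3 (18).

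The cost is some SAP wording and a few extra tables. Drug dispensing, pill counts, dose changes and AE onset dates are already recorded (Sections 8.5, 8.6.3 and 12.5.1), so no new visits or data are needed.

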### **13.7 Interim Analysis**

Not applicable

### **13.8 Data Monitoring Committee**

Not applicable

## 14 STUDY MANAGEMENT

### 14.1 Approval and Consent

#### 14.1.1 Regulatory Guidelines

This study will be conducted in accordance with the accepted version of the Declaration of Helsinki and/or all relevant federal regulations, as set forth in Parts 50, 56, 312, Subpart D, of Title 21 of the Code of Federal Regulations (CFR), and in compliance with GCP guidelines.

#### 14.1.2 Institutional Review Board/Independent Ethics Committee

Conduct of the study must be approved by an appropriately constituted IRB/IEC. Approval is required for the study protocol, investigational drug brochure, protocol amendments, informed consent forms (ICFs), and subject information sheets.

#### 14.1.3 Informed Consent

For each study subject, written informed consent will be obtained prior to any protocol-related activities. As part of this procedure, the Principal Investigator or one of his/her associates must explain orally and in writing the nature, duration, and purpose of the study, and the action of the drug in such a manner that the subject is aware of the potential risks, inconveniences, or adverse effects that may occur. The subject should be informed that he/she may withdraw from the study at any time, and the subject will receive all information that is required by local regulations and International Conference on Harmonization (ICH) guidelines. The PI will provide the Sponsor or its representative with a copy of the IRB/IEC-approved ICF prior to the start of the study.

Should changes to the Informed Consent form become necessary during the study, the PI will ensure that the changes are approved by the sponsor or its representative prior to submission to the IRB. All revisions of the protocol must be reflected in the IC form, if applicable, and reviewed by the IRB. Subjects must be made aware of those applicable changes in the protocol and must consent to participate in the revised protocol.

#### 14.1.4 Subject Confidentiality

All communications, reports, and subject samples will be identified by site number, and a code number and/or initials to maintain subject confidentiality. All records will be kept confidential to the extent permitted by law. If a waiver or authorization separate from the statement in the Informed Consent is required for permitting access to a subject's medical records (e.g. HIPAA), the Investigator will obtain such authorization prior to enrolling a subject in the study. The PI should keep a separate log of subjects, codes, names, and addresses. Documents which identify the subject by name (for example, the Informed Consent form) should be kept in strict confidence.

Suzhou Kintor Pharmaceutical, Inc.  
Protocol#: GT0918-US-1002

Proxalutamide (GT0918)

The sponsor and its business associates agree to keep all subject information confidential. Data resulting from analyses will be entered into a database that is not accessible to the public. Subject data will be identified only by the subject screen number, randomization number and initials, and not by any other annotation or identifying information.

The sponsor and its business associates will take every possible step to reduce the risk of releasing information to the public that would enable subjects to be personally identified.

#### **14.2 Data Handling**

Any data to be recorded directly on the eCRFs (to be considered as source data) will be identified at the start of the study. Data reported on the eCRF that are derived from source documents should be consistent with the source documents, or the discrepancies must be explained.

Clinical data will be entered on eCRFs for transmission to the Sponsor. Data on eCRFs transmitted via the web-based data system must correspond to and be supported by source documentation maintained at the study site, unless the study site makes direct data entry to the databases for which no other original or source documentation is maintained. In such cases, the study site should document which eCRFs are subject to direct data entry and should have in place procedures to obtain and retain copies of the information submitted by direct data entry. All study forms and records transmitted to the Sponsor must carry only coded identifiers such that personally identifying information is not transmitted. The primary method of data transmittal is via the secure, internet-based electronic data capture (EDC) system maintained by the Sponsor. Access to the EDC system is available to authorized users via the study's Internet web site, where an assigned username and password are required for access. The eCRFs will be considered complete when all missing and/or incorrect data have been resolved.

#### **14.3 Source Documents**

Source documents are considered to be all information in original records and certified copies of original records of clinical findings, observations, data or other activities in a clinical study necessary for the reconstruction and evaluation of the study. Source documents are filed and kept secure by the Investigator at each research site and can be obtained by contacting the Investigator to arrange access.

#### **14.4 Record Retention**

Study records and source documents must be preserved for at least 15 years after the completion or discontinuation of/withdrawal from the study or 2 years after the last approval of a marketing application in an ICH region, whichever is the longer time period.

The investigator agrees to comply with all applicable federal, state, and local laws and regulations relating to the privacy of subject health information, including, but not limited to, the

Standards for Individually Identifiable Health Information, 45 CFR, Parts 160 and 164 (the Health Insurance Portability Accountability Act of 1996 [HIPAA] Privacy Regulation). The Investigator shall ensure that study subjects authorize the use and disclosure of protected health information in accordance with HIPAA Privacy Regulation and in a form satisfactory to the Sponsor.

#### **14.5 Monitoring**

The study will be monitored to ensure that it is conducted and documented properly according to the protocol, GCP, and all applicable regulatory requirements.

On-site monitoring visits will be made at appropriate times during the study. Clinical monitors must have direct access to source documentation in order to check the completeness, clarity, and consistency of the data recorded in the eCRFs for each subject.

The Investigator will make available to the clinical monitor source documents and medical records necessary to complete eCRFs. In addition, the Investigator will work closely with the clinical monitor and, as needed, provide them appropriate evidence that the conduct of the study is being done in accordance with applicable regulations and GCP guidelines.

#### **14.6 Quality Control and Quality Assurance**

The Sponsor or its designee will perform the quality assurance and quality control activities of this study; however, responsibility for the accuracy, completeness, and reliability of the study data presented to the Sponsor lies with the Investigator generating the data.

The Sponsor will arrange audits as part of the implementation of quality assurance to ensure that the study is being conducted in compliance with the protocol, Standard Operating Procedures, GCP, and all applicable regulatory requirements. Audits will be independent of and separate from the routine monitoring and quality control functions. Quality assurance procedures will be performed at study sites and during data management to assure that safety and efficacy data are adequate and well documented.

